Sitnick M, Bodine SC & Rutledge JC. (2009). Chronic high fat feeding attenuates load-induced hypertrophy in mice. *J Physiol* 587, 5753-5765.

Protocol Title: Does Dapagliflozin Augment The Favorable Adaptation To Endurance Exercise Training?
Clinical Research Protocol Title: Dapagliflozin Augments The Favorable Adaptation To Endurance Exercise Training

Protocol Type: Biomedical

Date Submitted: 11/01/2018

Approval Period: 11/06/2018-11/05/2019

Important Note: This Print View may not reflect all comments and contingencies for approval. Please check the comments section of the online protocol.
Questions that appear to not have been answered may not have been required for this submission.
Please see the system application for more details.

Smith DA & O'Donnell TV. (1984). The time course during 36 weeks' endurance training of changes in Vo₂ max. and anaerobic threshold as determined with a new computerized method. Clin Sci (Lond) 67, 229-236.

b) Describe any animal experimentation and findings leading to the formulation of the study, if applicable.

See previous section (3a).

* * * Radioisotopes or Radiation Machines * * *

You selected NO for Radioisotopes in the General Checklist. If you would like to add Radioisotopes, change the selection to YES in general Checklist.

4.

Radioisotopes or Radiation Machines Please note: For projects requiring radiation procedures, please contact the CSU Radiation Control Office (RCO). For more information see:
<http://www.ehs.colostate.edu/WRad/Home.aspx> :

a) If applicable, summarize in lay language the radiographic diagnostic and therapeutic procedures associated with this protocol.

Body composition will be measured by dual energy x-ray absorptiometry (DEXA) on visit 1 and visit 50.

b)

Are the radiation procedures being performed a normal part of the clinical management for the medical condition that is under study (Standard of Care) or are the procedures being performed because the research subject is participating in this project (extra CT scans, more fluoroscopy time, additional Nuclear Medicine Studies, etc.,) (Not Standard of Care)? If some procedures are Standard of Care and some are Not Standard of Care, check both boxes.

NOT STANDARD OF CARE

If it is not standard of care, complete the rest of this section. Provide the CSU RCO approval information

X STANDARD OF CARE

If it is only standard of care, skip the rest of this section.

CSU Radiation Control Office approved protocol number:

Protocol Title: Does Dapagliflozin Augment The Favorable Adaptation To Endurance Exercise Training?
Clinical Research Protocol Title: Dapagliflozin Augments The Favorable Adaptation To Endurance Exercise Training

Protocol Type: Biomedical

Date Submitted: 11/01/2018

Approval Period: 11/06/2018-11/05/2019

Important Note: This Print View may not reflect all comments and contingencies for approval. Please check the comments section of the online protocol.
Questions that appear to not have been answered may not have been required for this submission.
Please see the system application for more details.

CSU Radiation Control Office protocol approval date:

For more information, see the RCO website at: <http://www.ehs.colostate.edu/Wrad/home.aspx> or Contact: [name], Radiation Safety Officer, at [contact].

*** Medical Equipment for Human Subjects and Laboratory Animals; Investigational Devices ***

5. Medical Equipment for Human Subjects

If medical equipment is being used for human subjects/patients, describe this equipment and indicate if the use is normal practice for the population under study. You may have already described this equipment in the Study Procedures section. If you have already listed this information in the Study Procedures Section, please do not duplicate this information here. In the space below, input N/A if not applicable, indicate if this is already listed in the Study Procedures Section, or describe the equipment.

N/A

6. Investigational Devices

Please list in the space below all Investigational Devices to be used on Subjects.

Investigational Devices

*** Drugs, Reagents, or Chemicals ***

7. Drugs, Reagents, or Chemicals

- a) Please list in the space below all investigational drugs, reagents or chemicals to be administered to subjects during this study.
- b) Please list in the space below all commercial drugs, reagents or chemicals to be administered to subjects during this study.

Protocol Title: Does Dapagliflozin Augment The Favorable Adaptation To Endurance Exercise Training?
Clinical Research Protocol Title: Dapagliflozin Augments The Favorable Adaptation To Endurance Exercise Training

Protocol Type: Biomedical

Date Submitted: 11/01/2018

Approval Period: 11/06/2018-11/05/2019

Important Note: This Print View may not reflect all comments and contingencies for approval. Please check the comments section of the online protocol.
Questions that appear to not have been answered may not have been required for this submission.
Please see the system application for more details.

Drug Name	Dapagliflozin (commercially known as Farxiga)
Source (e.g., Pharmacy, Sponsor, etc.,)	AstraZeneca Pharmaceuticals LP
If not premixed, where will the material be mixed and by whom	Pre-mixed by Bristol-Myers Squibb Company
Manufacturer	Bristol-Myers Squibb Company
IND # (if available)	To be submitted
Dosage	5 mg/day of Dapagliflozin for the first 14-days, and then a dose increase to 10 mg/day of Dapagliflozin for remaining 10 weeks.
Administration Route	Oral
Y	Are these new or different uses of these commercially available drugs, reagents, or chemicals?
Y	IND Regulations

Please read the IND Statements

*** Subject Population (a-g) ***

8.

Subject Population - In the space below, please detail the participants that you are requesting to recruit (include requested participant number and description of each group requested). (Input N/A if not applicable)

a) **Requested Participant Description (Include number of participants that you plan to study and description of each group requested, if applicable).**

We plan on enrolling 60 participants with estimation that 50% will screen out or not complete the study. We plan to complete the study in 30 overweight/obese adult volunteers (men and women).

b) **What is the rationale for studying the requested group(s) of participants?**

Adults who are overweight/obese are at the greatest risk of developing type 2 diabetes, thus overweight/obese adults potentially have the most to gain should the outcome of the study prove

Protocol Title: Does Dapagliflozin Augment The Favorable Adaptation To Endurance Exercise Training?
Clinical Research Protocol Title: Dapagliflozin Augments The Favorable Adaptation To Endurance Exercise Training

Protocol Type: Biomedical

Date Submitted: 11/01/2018

Approval Period: 11/06/2018-11/05/2019

Important Note: This Print View may not reflect all comments and contingencies for approval. Please check the comments section of the online protocol. Questions that appear to not have been answered may not have been required for this submission. Please see the system application for more details.

favorable. Inclusion of adults already diagnosed with diabetes might complicate the interpretation of the data; that is, as a consequence of the patho-physiology associated with diabetes, the response to exercise training with or without Dapagliflozin may differ in adults with diabetes compared with adults who are diabetes free.

c) If applicable, state the rationale for involvement of potentially vulnerable subjects to be entered into the study, including minors, pregnant women, economically and educationally disadvantaged, or decisionally impaired subjects. Specify the measures being taken to minimize the risks and the chance of harm to the potentially vulnerable subjects.

Potentially vulnerable subjects will not be studied.

d) If women, minorities, or minors are not included, a clear compelling rationale must be provided. Examples for not including minors: disease does not occur in children; drug or device would interfere with normal growth and development; etc.

Women and minorities will be invited to participate. Minors will be excluded. The prevalence of type 2 diabetes is greater in adults than minors. Safety and effectiveness of Dapagliflozin in pediatric patients under 18 years of age have not been established.

e) State if any of the subjects are students, employees, or laboratory personnel. They should be presented with the same written informed consent. If compensation is allowed, they should also receive it.

If any of the subjects are students, employees, or laboratory personnel they will be presented with the same written informed consent; compensation is allowed, they will also receive it.

f) Describe how potential subjects will be identified for recruitment (e.g., chart review, referral from individual's treating physician, those individuals answering an ad). How will potential participants learn about the research and how will they be recruited (e.g., flyer, email, web posting, telephone, etc.)? Attach recruitment materials in the Attachment Section (#16). Important to remember: potential subjects may not be contacted before IRB approval.

Please see examples of recruitment materials in the attachment section.

Potential subjects will be recruited via electronic advertisement (e.g. The Source) and email lists (e.g. CSU genfac). If necessary, potential subjects may also be recruited via newspaper advertisement (e.g. The Coloradoan), clinical trials websites (e.g. clinicaltrials.gov), and/or flyers/posters placed in public places (e.g. coffee shops) in and around the Fort Collins area.

g) If applicable, provide rationale for the inclusion of healthy volunteers in this study. Specify any risks to which these healthy volunteers may possibly be exposed. Specify the measures being taken to minimize the risks and the chance of harm to these volunteers.

Adults who are overweight/obese but otherwise healthy will be invited to participate. Inclusion of adults already diagnosed with diabetes might complicate the interpretation of the data; that is, as a consequence of the patho-physiology associated with diabetes, the response to exercise training with or without

Protocol Title: Does Dapagliflozin Augment The Favorable Adaptation To Endurance Exercise Training?
Clinical Research Protocol Title: Dapagliflozin Augments The Favorable Adaptation To Endurance Exercise Training

Protocol Type: Biomedical

Date Submitted: 11/01/2018

Approval Period: 11/06/2018-11/05/2019

Important Note: This Print View may not reflect all comments and contingencies for approval. Please check the comments section of the online protocol. Questions that appear to not have been answered may not have been required for this submission. Please see the system application for more details.

Dapagliflozin may differ in adults with diabetes compared with adults who are diabetes free.

It is not possible to identify all potential risks in research procedures, but the researcher(s) have taken reasonable safeguards to minimize any known and potential (but unknown) risks. The Human Performance Clinical Research Laboratory has emergency supplies including a medicine trolley equipped with heart machines and supplemental oxygen. The research team has a great deal of experience with all of the procedures. Some of the procedures for which you are being asked to volunteer have a number of associated risks:

Body Composition

The risks associated with the DEXA are very low. The maximum radiation dose you will receive in this study is less than 1/1000th of the federal and state occupational whole body dose limit allowed to radiation workers (5,000 mrem). Put another way, the maximum dose from any scan we utilize with this DEXA ranges from 1.2 mrem (Whole body scan) to 12.2 mrem (for several of the regional scans, such as lumbar, femur, and forearm scans). The average annual background radiation you already receive is at least 620 mrem/year. The more radiation you receive over the course of your life, the more the risk increases of developing a fatal cancer or inducing changes in genes. The radiation in this scan is not expected to significantly increase these risks, but the exact increase in such risks is not known. There are no discomforts associated with this procedure. Women who are or could be pregnant should receive no unnecessary radiation and should not participate in this study.

Women will complete a pregnancy test before participating in a DEXA scan.

Exercise Tests and Exercise Training

There is a very small chance of an irregular heartbeat during exercise (< 1% of all subjects). Other rare risks of a stress test are heart attack (< 5 in 10,000) and death (<2 in 10,000). Wearing a mouthpiece and nose-clip can sometimes cause dryness in the mouth and mild discomfort. Difficult exercise may make you feel very tired, light headed and nauseous. Exhausting exercise will, by definition, make you feel very tired. After any exercise your muscles might ache.

ACSM guidelines pertinent to the requirement of physician supervised exercise (stress) testing will be followed.

Blood Collection

When the needle goes into a vein, it may hurt for a short period of time (a few seconds). Also there may be minor discomfort of having the needle/plastic tube taped to your arm. In about 1 in 10 cases, a small amount of bleeding will occur under the skin that will cause a bruise. The risk of forming a blood clot in the vein is about 1 in 100, and the risk of significant blood loss is 1 in 1,000. Additionally, there is a risk that you may faint while having blood collected or having the catheter inserted in your vein.

Only trained research personnel will be permitted to perform phlebotomy.

Muscle Biopsy

During the procedure you may feel discomfort associated with the injection of the numbing drug (the anesthetic) but during the actual muscle removal the discomfort should be minimal. There is a risk that you may faint during the procedure. There is also a risk of muscle cramp, bleeding, of loss of feeling in your leg, and of damage to a skin (cutaneous) nerve. The risk of infection and bruising is extremely small if you follow the instructions for caring for the incision. A very small and minor scar will remain as a result of the incision, but may not be noticeable. These procedures will be performed under surgically clean conditions.

Protocol Title: Does Dapagliflozin Augment The Favorable Adaptation To Endurance Exercise Training?
Clinical Research Protocol Title: Dapagliflozin Augments The Favorable Adaptation To Endurance Exercise Training

Protocol Type: Biomedical

Date Submitted: 11/01/2018

Approval Period: 11/06/2018-11/05/2019

Important Note: This Print View may not reflect all comments and contingencies for approval. Please check the comments section of the online protocol.
Questions that appear to not have been answered may not have been required for this submission.
Please see the system application for more details.

Emergency medical equipment will be available. You will be screened prior to the procedure for history of allergic reactions to Novocain (Lidocaine).

Only trained research personnel will be permitted to perform muscle biopsies.

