*** Continuing review ***

To renew your protocol: 1. Complete this one-page form; 2. If necessary, update any sections of the protocol that need to be updated for the upcoming year (e.g., change in personnel, location); 3. Electronically "sign" the application by clicking in the check box on the bottom of the "Obligations" page; 4. Remember to click "Submit Form" and confirm your intent to submit by clicking "OK" so that the IRB administrators receive your application. You must answer each question. Input N/A to answer any questions that are not applicable. NOTE: Documents that contain much of the information required to answer the participant number questions below can be found in the "Event History" section of each protocol. The status on your homepage will be "Submitted to IRB" when your submission is successful. IMPORTANT: If the Department Head has changed since your last approval, please be sure to update the Department Head listing on the personnel information screen of your protocol.

1. Summary: Number of Participants Associated with the Protocol:

a. Total number of participants approved to date:

60

b. Number of participants studied since the last approval date:

0

c. Total number of participants studied since the beginning of the project:

57

d. Number of participants remaining to study (total number of participants approved LESS the total number of participants studied to date):

3

e. Please explain if there is a discrepancy in participant numbers (e.g., more participants responded to a survey than had been approved):

2. a. Reasons and number of withdrawals from the research (both subject and investigator initiated) since the last approval date.

none studied since last approval

Protocol Title: Does Dapagliflozin Augment The Favorable Adaptation To Endurance Exercise Training?
Clinical Research Protocol Title: Dapagliflozin Augments The Favorable Adaptation To Endurance Exercise Training

Protocol Type: Biomedical

Date Submitted: 11/01/2018

Approval Period: 11/06/2018-11/05/2019

Important Note: This Print View may not reflect all comments and contingencies for approval. Please check the comments section of the online protocol. Questions that appear to not have been answered may not have been required for this submission. Please see the system application for more details.

b. **Number of subjects lost to follow-up since the beginning of the study.**

4

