a) In lay language, describe all the procedures, from screening through end-of-study, that the human subject must undergo in the research project, including study visits, drug treatments, randomization and the procedures that are part of standard of care. Please note: Do NOT respond "See Attachment Section." If you would like to add tables, charts, etc., attach those files in the Attachment section (#16).

OVERVIEW

This is a randomized, placebo-controlled, double blind, repeated measures study. 30 sedentary adults will be recruited for participation and randomly assigned to one of two 12-week treatments: 1) supervised endurance exercise training 4 days per week plus daily oral administration of Dapagliflozin; 2) supervised endurance exercise training 4 days per week plus daily oral administration of placebo. Prior to and following completion of the treatment the following dependent variables will be quantified: a) maximal aerobic capacity; b) substrate utilization during standardized low-moderate intensity exercise; c) skeletal muscle aerobic enzyme activity; d) body composition; and, e) oral glucose tolerance, fasting glucose and insulin resistance.

Study participants will report to the Human Performance/Clinical Research Laboratory (HPCRL) on 51 separate occasions:

Visit 1: study participants will undergo screening: medical history, 12-lead electrocardiogram and blood pressure assessment at rest and during incremental exercise to volitional exhaustion, blood sampling, and measurement of body composition.

Visit 2: maximal oxygen uptake will be measured.

Visit 3: the metabolic response to standardized exercise will be determined.

Visit 4: an oral glucose tolerance test will be performed, and then skeletal muscle will be sampled.

Visits 5-48: 12 weeks of supervised exercise training. Concurrent with these visits, research participants will ingest, on a daily basis, either Dapagliflozin or placebo.

Visit 49: maximal oxygen uptake and body composition will be measured.

Visit 50: the metabolic response to standardized exercise will be determined.

Visit 51: an oral glucose tolerance test will be performed, and then skeletal muscle will be sampled.

DETAILED DESCRIPTION OF STUDY PROCEDURES

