Clinical Research Protocol Title: Dapagliflozin Augments The Favorable Adaptation To Endurance Exercise Training

Protocol Type: Biomedical

Date Submitted: 11/01/2018

Approval Period: 11/06/2018-11/05/2019

Important Note: This Print View may not reflect all comments and contingencies for approval. Please check the comments section of the online protocol.
Questions that appear to not have been answered may not have been required for this submission.
Please see the system application for more details.

11/29/2017	CONTINUING REVIEW 3 FORM APPROVED	Y	Y
11/01/2018	CONTINUING REVIEW 4 FORM CREATED		
11/01/2018	CONTINUING REVIEW 4 FORM SUBMITTED	Y	
11/06/2018	CONTINUING REVIEW 4 FORM APPROVED	Y	Y

Methods of statistical analyses

Two-way analysis of variance (before training *vs.* after training, and Dapagliflozin *vs.* Placebo) with repeated measures on one factor (before *vs.* after) are used to examine differences in primary outcomes resulting from exercise training and/or drug treatment. Multiple comparisons of factor means will be performed using the Newman-Keuls test.

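### As planned, the ANOVA's arm-by-time test of the drug effect is a change-score t-test; adjusting the final value for baseline is usually more precise and costs almost nothing

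*Combined protocol and SAP*

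**What the plan says.** The statistical text is two sentences under Methods of statistical analyses, at the end of the document after Event History. It specifies a two-way ANOVA crossing time (before, after) with arm (dapagliflozin, placebo), "with repeated measures on one factor". These models "are used to examine differences in primary outcomes resulting from exercise training and/or drug treatment". Newman-Keuls comparisons follow. The text names no baseline covariate, no term that tests the drug effect, no analysis set and no rule for missing final values.

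The Overview under Study Procedures sets the measurement times: "Prior to and following completion of the treatment the following dependent variables will be quantified". For maximal oxygen uptake the baseline is Visit 2, and the final value comes at the visit described as "Visit 49: maximal oxygen uptake and body composition will be measured".

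On numbers, the Overview says "30 sedentary adults will be recruited for participation and randomly assigned to one of two 12-week treatments". Subject Population a) says "We plan on enrolling 60 participants with estimation that 50% will screen out or not complete the study", and then gives 30 as the number in whom the study is to be completed. The Continuing review form reports 60 approved and 57 studied. Its item "Number of subjects lost to follow-up since the beginning of the study" is answered 4, with no arm or timing. Item 4 of that form says that recruitment has ended, interventions are complete and only data analysis remains.

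**The concern.** The trial asks whether the drug augments the response to training. In a time-by-arm ANOVA, that question is answered by the arm-by-time term. With only two time points, this term compares mean change between arms and so fixes the weight on baseline at 1. A regression estimates that weight from the data, which usually gives a smaller standard error. In a trial of about 30 people with data collection finished, the analysis is one of the few places left to gain precision.

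Two smaller matters go with this. Because the term is not named, a reader could take the drug main effect as the test, which would be much weaker. And 30 serves both as the number randomised and as the number completing, although Subject Population a) expects some people not to complete.

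**Working it through.** **1. The plan's own figure.** 60 x (1 - 0.5) = 30, so the enrolment arithmetic reproduces. The 50% is not split into losses before and after randomisation, so the number randomised does not follow from it. For 30 completing, one would randomise 34, 38 or 43 at assumed post-randomisation losses of 10%, 20% or 30%.

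**2. Inputs.** From the documents: two arms, one assessment before and one after, 30 completing, no baseline covariate. Assumed, because not stated: 15 v 15 analysed, equal variance before and after, two-sided 5%, 80% power, and a range for the pre-post correlation rho. Where an outcome has several readings within a visit, the argument applies to each reading or summary.

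**3. Identity.** With two time points the arm-by-time F equals the square of the t statistic on change. On one simulated data set both were 2.7041.

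**4. Variance of the drug estimate.** With outcome variance s^2 and N analysed in equal arms:

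- Change score: (4/N) x 2 s^2 (1 - rho)
- Baseline-adjusted: (4/N) x s^2 (1 - rho^2) x (N - 3)/(N - 4), where the last factor is the average cost of chance baseline imbalance
- Ratio: (1 + rho)/2 x (N - 3)/(N - 4). At N = 30 this is (1 + rho)/2 x 27/26

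| rho | Ratio | Change in variance | Equivalent change-score N (30/ratio) | Detectable effect, adjusted (SD of change) |
|---|---|---|---|---|
| 0.5 | 0.75 x 1.0385 = 0.779 | -22% | 38.5 | 0.937 |
| 0.7 | 0.85 x 1.0385 = 0.883 | -12% | 34.0 | 0.997 |
| 0.9 | 0.95 x 1.0385 = 0.987 | -1% | 30.4 | 1.054 |
| 0.95 | 0.975 x 1.0385 = 1.012 | +1% | 29.6 | about 1.07 |

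The change-score test (28 df) detects 1.060 SD of change; the adjusted test has 27 df. Simulated ratios (40,000 trials per setting) were 0.781, 0.888, 0.987 and 1.012. Break-even is at (1 + rho)/2 = 26/27, so rho = 0.926. The ratio cannot exceed 27/26 = 1.038, so the most that adjustment can cost is about 4% in variance. At the effect where the change-score test has 80% power, the adjusted test has 88.7%, 84.6% and 80.4% at rho 0.5, 0.7 and 0.9.

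**5. If the drug main effect were used instead.** It averages before and after values and so halves the effect. For a true difference of 0.5 outcome SD at N = 30, its power is 10% to 13% for rho between 0.3 and 0.95. Arm-by-time has 26%, 40% and 84% at rho 0.5, 0.7 and 0.9.

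**6. Missing final values.** In a simulated set of 34 with 4 final values missing, a constrained mixed model fitted to all 34 gave a drug estimate of 0.12630. The regression in the 30 with both values gave 0.12630. People with only a baseline therefore add nothing to the estimate under either model. Filling in single predicted values as if observed is unsafe: with 17 v 17, 4 missing at random and no true effect, type I error was 8.3-8.9%, against 4.8-5.1% in those with both values.

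**7. Dropout bias, illustration only.** Suppose 17 v 17 are randomised, 4 are lost, there is no true effect, and dropout correlates 0.3-0.5 with response. The change-score estimate is then biased by 0.11-0.19 SD of change (type I error 6-9%) if all four losses are in one arm, by 0.05-0.09 SD (5-6%) with a 3-1 split, and not at all with 2-2. If loss is unrelated to arm, these splits have chances of 10%, 50% and 40%. Baseline adjustment still leaves 0.09-0.18 SD in the 4-0 case.

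**The case against.** The change-score test is valid under randomisation, so the issue is efficiency and not error. The gain depends on a correlation that the documents do not give; for a highly reproducible outcome it could be nil or slightly negative. Changing the drug-effect test after the data are in has a credibility cost of its own. All of this stands. It limits the size of the point and is why the ANOVA should still be reported.

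The document is an ethics-committee form. Its attachment list includes two sponsor's protocol files that are not visible, and its references include a paper on power for repeated-measures linear models that no visible text cites. A sample-size calculation or a fuller analysis plan may exist there. That also stands, so no claim is made that either is absent from the trial.

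Three stronger readings are tempting, and the documents do not support them:

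- *The ANOVA is at fault for leaving out people without a final value.* The regression leaves out the same people, so this does not separate the two methods.
- *The planned size cannot be determined.* Subject Population a) gives 60 enrolled and 30 completing, and the Continuing review form confirms 60 approved. The Overview answers a request for lay language and may use 30 loosely. Only the number randomised is unclear.
- *The four losses have biased the drug effect.* Nothing ties them to an arm or to the period after randomisation, and 17 v 17 with 4 lost appears nowhere in the documents.

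**Conclusion.** The point holds as one of precision. Read as the arm-by-time term, the planned test is a change-score t-test, and baseline adjustment would usually improve on it using data already collected. The gain is worth having at correlations of 0.5 to 0.7 (equivalent to about 4 to 8 extra people), negligible at 0.9, and gone above about 0.93. These figures assume 15 v 15 analysed and equal variances.

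Adjustment does not address missing final values or dropout bias; those need a separate sensitivity analysis if anyone randomised lacks a final value. The double use of 30 is a minor wording correction.

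**What to change.** 1. In Methods of statistical analyses, state that the drug effect on each outcome is estimated by regressing the final value on baseline and arm, in assigned arms, for everyone randomised with a final value. Keep the ANOVA as supportive and name arm-by-time as its drug-effect term. If results by arm have already been seen, label the change post hoc and report both.
2. If any randomised participant lacks a final value, add a sensitivity analysis: multiple imputation from baseline and arm, shifts applied separately in each arm (for example -1 to +1 SD of change), and standard errors that reflect the imputation. Single predicted values must not be treated as observed. In the one-arm-loss illustration above, the lost values lay 0.36-0.79 SD below prediction, so this range covers them.
3. In the Overview and in Subject Population a), give the numbers screened, randomised and completing separately, consistent with the sponsor's protocol in the attachment list. Report them by arm, with the timing of each loss.

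Cost: one regression per outcome, one degree of freedom (28 to 27 with 30 analysed), and no gain or a very small loss if the correlation exceeds about 0.93. If final values are missing, one sensitivity table is added. A protocol amendment is needed, since the Obligations section requires changes to be approved before they are made. No new visits or data are required.
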